1.1 Rationale for Proposed Study

1.1.1 Significance of the Condition

Breast cancer is one of the most prevalent cancers with 207,090 new cases of breast cancer and 39,840 deaths in women predicted for 2010 in the United States⁽¹⁾. Aromatase inhibitors (AIs) are used as first-line adjuvant therapy for postmenopausal women with early stage breast cancer⁽²⁾. The effectiveness of current therapy is widely recognized to be compromised by poor compliance because of aromatase inhibitor-associated musculoskeletal symptoms (AIMSS), a syndrome that affects up to 40-50% of women who take these medications. The syndrome that was not recognized during the registration trials for this class of drugs⁽³⁾, it can lead to discontinuation in up to 24% of women over 2 years ^(4,5). Knowledge that can be used to prevent discontinuation of these important agents because of severe AIMSS is urgently needed.

The NCI Division of Cancer Prevention has recognized AIMSS as a priority area for future study. The symptoms are associated with a high rate of AI discontinuation and therefore compromise survival outcomes at great cost to both patients and society. Very little is known about AIMSS, or how to predict who is at risk for the condition, or for discontinuing therapy because of the symptoms. This study will provide a basis for comprehensive assessment of risk factors at the patient-reported outcomes, phenotypic, and laboratory levels. We will explore the natural history of AIMSS in different ethnic populations, and will validate previously reported genetic determinants of the development of AIMSS.

A common problem with multicenter GWAS studies of very large sample size, especially in the absence of measurable diagnostic parameters, is inclusion of heterogeneous groups of patients⁽⁶⁾. In addition to assessing pharmacogenomic predictors, this study involves specification of a pre-defined AIMSS phenotype and collection of patient-reported outcomes (PROs). As such, these data will have clinical utility by clarifying the factors associated with aromatase inhibitor discontinuation and thus guiding clinicians towards interventions to improve adherence. Coupled with other studies, the long-term goals are to develop a gene signature that will be used to better guide the selection of endocrine interventions for patients with breast cancer.

Etiology and Pathophysiology

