The exemestane and letrozole pharmacogenomics (ELPh) study, conducted by the Consortium on Breast Pharmacogenomics (COBRA), has provided important data not only regarding the prevalence of the symptoms and drug discontinuation but also for PRO by using the Health Assessment Questionnaire (HAQ), a commonly used rheumatology instrument. [name] and [name] of ECOG are co-founders of the COBRA group. In this prospective comparison of exemestane and letrozole, patients were randomly assigned to either letrozole or exemestane and were evaluated at predefined intervals by study team members and referred to a rheumatologist based upon change in HAQ scores and pain ratings on a visual analog scale (VAS). The study showed that the predefined symptomatic criteria based on the HAQ and VAS successfully provided a means of case definition of an otherwise difficult-to-characterize syndrome (4,5). Improvement or worsening of HAQ score was defined as a decrease or increase, respectively, of more than 0.22 based on data provided from the rheumatology literature⁽¹²⁾. However, the sensitivity, specificity, and generalizability of the ELPh clinical criteria for defining AIMSS clearly need to be confirmed in a larger cohort of a diverse patient population and in other clinical settings. Data from the ELPh study for the first 100 patients showed that median time to onset of symptoms was 1.6 months (range 0.4-10 months), and median time to study discontinuation (for those who stopped taking AI) was 6.1 months (range 2.2-13 months) (4).

Anastrozole was not studied in the ELPh trial, representing a gap in knowledge both as it is a widely prescribed AI, and because anastrozole associated musculoskeletal symptoms have not been phenotypically characterized with the HAQ. Furthermore, as the patients studied by the ELPh and NCIC Clinical Trials Group MA.27 (described below) populations are predominantly Caucasian, further studies in minority populations are urgently needed.

Genetic Predictors of AIMSS: Pharmacogenomic predictors may help identify women at risk for AIMSS since genetic variants that are associated with AI pharmacokinetics, with the effects of estrogen deprivation on bone and other phenotypes have already been described. We briefly review recent important findings that emphasize the importance of this concept as well as its feasibility.

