8.1.11 References

AstraZeneca. Arimidex (anastrozole) tablets prescribing information. Wilmington, DE; 2008 Dec.

9. Statistical Considerations

The primary endpoint is defined as discontinuation of treatment following development of AIMSS. A patient will be considered to have developed AIMSS if there is a 20% or greater decline in scores on the HAQ instrument from baseline within one year. At the time of treatment discontinuation, patients and providers will be asked to rank the reasons for treatment discontinuation. If either the patient or the provider lists pain as the first or second-ranked reason and discontinuation is within 3 months of symptom escalation, this will be considered an event. Patients who are lost to follow-up or whose reason for discontinuation is unknown will be considered to be event-free. From previous studies, it is estimated that 40% of patients will develop symptoms, and 25% of patients will discontinue treatment with Als within 1 year due to development of musculoskeletal symptoms.

The enrollment plan is designed to assure adequate enrollment of minority (Asian and African-American) patients. After 600 patients are enrolled from other racial groups, closure of the study to those subgroups will be terminated and accrual will continue among only Asian and African-American patients. When 200 patients are enrolled from the first remaining racial subgroup, closure of accrual to that subgroup will terminate and all remaining patients will be enrolled from the final remaining subgroup. ECOG Minority CCOPs will be strongly encouraged to participate in order to meet targets for minority accrual. While not a separate accrual cohort, ethnicity (Hispanic/non-Hispanic) will also be considered in the analysis plan.

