9.1 Statistical considerations for primary objective of SNP validation

Patients will be classified into two groups based on whether or not they discontinued treatment due to MSS. Hardy-Weinberg equilibrium will be evaluated within each racial subset. SNP genotypes will be coded as additive effects on the log odds ratio by coding as 0, 1 or 2 for the count of the minor allele. Logistic regression will be used to test the association between having a minor allele and the log odds of discontinuation of treatment, adjusting for covariates. We plan to enroll 1000 patients and follow them for development of symptoms. Minor allele frequencies reported by Ingle et al. were assumed for the 4 SNPs associated with the TCL1A gene, and preliminary results from the ELPH study were used to estimate minor allele frequencies associated with the ESR gene. A Bonferroni adjustment will be used to account for the simultaneous testing of 10 SNPs; a one-sided p-value of 0.0025 will be considered statistically significant. For purposes of illustrating statistical power, we assume that Hardy-

Weinberg equilibrium exists in the allele distribution and that the minor allele is associated with *higher* proportions of discontinuation of treatment due to development of symptoms. Table 1 shows the genes, SNPs, and representative minor allele frequencies observed in previous studies. Table 2 shows odds ratios for the effect of each minor allele that will be detectable with 80% power for overall discontinuation rates of 20% or 30% and a range of plausible minor allele frequencies, given a sample size of 1000 patients and using a one-sided Cochran-Armitage trend test. The table also shows detectable odds ratios for the subsets of Caucasian (n=600) and African-American and Asian patients (n=200 patients each).

Table 1. SNPs to be validated

SNP	Gene	Rank (Ingle)	Rank (ELPH)	Minor Allele Frequency (MAF)
rs7158782	TCL1A	1		0.189 among cases, 0.109 among controls (0.2 ELPH)
rs7159713	TCL1A	2		0.189 (0.19 ELPH)
rs2369049	TCL1A	3	4	0.176 (.18 ELPH)
rs11849538	TCL1A	4	9	0.15 (ELPH)
rs2296972	HTR2A		1	0.37 (ELPH)
rs2347868	ESR1		2	0.23
rs9340835	ESR1		3	0.35
rs2234693	ESR1			0.45 (Riancho)
rs1062033	CYP19A1			0.44 (Riancho)
rs4646	CYP19A1		5	0.28

Table 2. Odds Ratios for Effect of Each Minor Allele Detectable with 80% Power (Additive Model)

Proportion Discontinuing	MAF	N=1000	N=600	N=200
20%	10%	1.88	2.23	3.89
30%	10%	1.78	2.10	3.65
20%	20%	1.63	1.87	2.94
30%	20%	1.55	1.76	2.70

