10.2.4 Scoring

Genotyping data results will yield one of three possible classifications: Homozygous wild-type (2 wild-type alleles), heterozygous (1 wild-type and 1 variant allele), or homozygous variant (2 variant alleles). The classification is determined based on the fluorescent values obtained from the allelic discrimination plots of the Taqman™ assays. These are standard assays used widely in the field for genotyping. Minor allele frequencies are expected to range from 10% to 38% based on prior studies in similar populations. This range of frequencies is high enough that an association between the polymorphism and the phenotype of treatment discontinuation due to AIMSS has potential utility. The rate of treatment discontinuation due to AIMSS is expected to be 20 to 30%.

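### Does a planned 25% one-year AIMSS discontinuation rate, set against a background figure of up to 24% over two years, undermine the power table?

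*Combined protocol and SAP*

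**What the plan says.** Section 9 sets the planning rate: "it is estimated that 40% of patients will develop symptoms, and 25% of patients will discontinue treatment" with AIs "within 1 year due to development of musculoskeletal symptoms". It attributes this to previous studies without a citation. The same section defines the event. It requires a 20% or greater decline on the HAQ, pain ranked first or second among the reasons for stopping by either patient or provider, and stopping within 3 months of symptom escalation. It adds: "Patients who are lost to follow-up or whose reason for discontinuation is unknown will be considered to be event-free".

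Section 9.1 does not use 25% directly. Table 2 lists odds ratios "detectable with 80% power for overall discontinuation rates of 20% or 30" per cent, for minor allele frequencies (MAF) of 10 to 40% and N of 1000, 600 and 200. It assumes a one-sided Cochran-Armitage trend test and a threshold of 0.0025, and it is offered as an illustration of power. Section 10.2.4 repeats the range: "The rate of treatment discontinuation due to AIMSS is expected to be 20 to 30" per cent.

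The background in Section 1.1.1 says of AIMSS that "it can lead to discontinuation in up to 24% of women over 2 years", citing references 4 and 5. It also reports, for the first 100 patients of the ELPh study, a median time to discontinuation of 6.1 months (range 2.2 to 13) among those who stopped.

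**The concern.** Cumulative discontinuation cannot fall with time. If both figures described the same event in the same kind of patient, 25% at one year could not sit beneath a maximum of 24% at two years. The 30% rows would then be 6 percentage points too high, and even the 20% rows would need at least 20/24 = 83% of two-year stopping to occur in year 1 and still meet the Section 9 definition.

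Table 2 is the only power statement for the primary objective. If the true one-year rate were well below 20%, the study would have less power than any row suggests. A SNP that missed significance might then be read as not validated at an effect the study could not reliably detect.

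**Working it through.** **Inputs.** From Section 9.1: N = 1000, one-sided alpha 0.0025 (z = 2.807), allele count coded 0/1/2, Hardy-Weinberg proportions, overall rates K of 20% and 30%. From Section 9: K = 25%. From Section 1.1.1: 24% as the two-year maximum.

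**Formula.** Genotype frequencies are g = ((1−m)², 2m(1−m), m²) for MAF m. The genotype-specific risks follow logit p_i = b + i·ln(OR), with b solved so that the overall rate is K. Let d be the difference in mean allele count between patients with and without the event, n1 = NK and n0 = N(1−K). Then

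- s0 = √[V(1/n1 + 1/n0)], with V = 2m(1−m)
- s1 = √[V1/n1 + V0/n0], with V1 and V0 the allele-count variances in the two groups
- power = Φ[(d − 2.807·s0)/s1]

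No continuity correction is applied; the protocol does not say whether Table 2 used one.

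**Step 1: reproduce Table 2.** For MAF 20%, K = 30% and OR 1.55: d = 0.1455, s0 = 0.03904, s1 = 0.04073. Power = Φ[(0.1455 − 0.1096)/0.04073] = Φ(0.88) = 81.1%. Across the eight N=1000 cells the stated odds ratios give 80.5 to 81.7%. The odds ratios detectable with exactly 80% power agree with Table 2 to within 0.02. The table is right for its inputs.

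**Step 2: size of the documented gap.** Odds ratio detectable with 80% power at N=1000:

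| Rate | MAF 10% | 20% | 30% | 40% |
|---|---|---|---|---|
| 25% | 1.799 | 1.574 | 1.496 | 1.466 |
| 24% | 1.809 | 1.582 | 1.504 | 1.474 |
| Difference | 0.010 | 0.008 | 0.008 | 0.008 |

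**Step 3: power at the odds ratios Table 2 prints.** For the 30%-row value at MAF 20% (OR 1.55) and K = 24%: d = 0.1479, s0 = 0.04189, s1 = 0.04434. Power = Φ[(0.1479 − 0.1176)/0.04434] = Φ(0.68) = 75.3%. All cells (%):

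| Odds ratios taken from | True rate | MAF 10% | 20% | 30% | 40% |
|---|---|---|---|---|---|
| 30% rows (1.78/1.55/1.47/1.44) | 30% | 81.7 | 81.1 | 80.5 | 80.6 |
| 30% rows | 25% | 78.2 | 76.5 | 75.3 | 74.9 |
| 30% rows | 24% | 77.2 | 75.3 | 73.9 | 73.4 |
| 20% rows (1.88/1.63/1.55/1.52) | 24% | 85.7 | 85.9 | 86.6 | 87.1 |

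Most of the shortfall in the 30% rows is already there at the protocol's own 25%, because 30% is the upper end of a bracket. Going on to 24% costs a further 1.0 to 1.5 points.

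**Step 4: rates below the bracket, as assumptions only.** At 15%, the 20%-row odds ratios have 69.5 to 73.0% power. A constant hazard that gives 24% at two years implies 1 − √0.76 = 12.8% at one year, and power of 62.0 to 67.4%.

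**Step 5: does the quoted timing favour such rates?** That constant hazard is h = −ln(0.76)/24 = 0.01143 per month. The median stopping time among two-year stoppers would be −ln(0.88)/h = 11.2 months, and 42% of them would stop after month 13. Section 1.1.1 reports a median of 6.1 months and a maximum of 13. Follow-up of those 100 patients is not stated, so this is not proof. It is the only timing evidence in the documents, and it points to stopping concentrated in year 1.

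**The case for a change.** The best case for a change is that the planning rate has no source, half of Table 2 sits above the only referenced rate in the protocol, and no row lies below 20%. Early stopping can bring the one-year rate close to 24% but cannot lift it above. The ELPh timing comes from 100 patients in a study without anastrozole. The Section 9 definition adds uncertainty: the HAQ criterion, the 3-month window and the event-free rule all lower the counted rate, while accepting either party's ranking raises it, and the net effect is not quantified. Restating the text would be cheap.

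The missing source and the absence of a reconciling sentence stand. The claim of a true contradiction is weaker. The 24% is cited to references 4 and 5; Section 1.1.1 describes that earlier work as a letrozole and exemestane study in a predominantly Caucasian population. This cohort takes anastrozole and plans 400 Asian and African-American patients among 1000. The 25% is credited to previous studies in the plural, and MA.27 and E1Z03 were also in view. The 24% is therefore a background figure and does not cap the rate here. Dropping the 30% rows or capping the rate at 24% would rank one figure above another without sight of either source.

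**Conclusion.** The two rates are unreconciled, but this is a gap in sourcing with no practical gain from amending the plan. Table 2 is correct for its stated rates and brackets both figures. The difference between 24% and 25% moves the N=1000 detectable odds ratio by about 0.01, and a reader who uses the 20% rows at a true 24% is on the conservative side, with about 86 to 87% power. The 30% rows are the favourable end of a labelled range, and their odds ratios have roughly 73 to 78% power at 24 or 25%.

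Nothing operational depends on the rate. N = 1000 is the sum of the cohort targets 600 + 200 + 200, the threshold is fixed at 0.0025, and the analysis will use the events observed. A non-significant SNP can be judged on its estimated odds ratio and confidence interval, whatever rate was assumed beforehand.

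The conclusion assumes that the one-year rate under the Section 9 definition is not far below 20%. If it were 15%, power at the 20%-row odds ratios would be about 70 to 73%. The documents neither state nor favour such a rate, and with enrolment, test and decision rule unchanged, an extra illustrative row would not alter the results.

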9.1 Statistical considerations for primary objective of SNP validation

Patients will be classified into two groups based on whether or not they discontinued treatment due to MSS. Hardy-Weinberg equilibrium will be evaluated within each racial subset. SNP genotypes will be coded as additive effects on the log odds ratio by coding as 0, 1 or 2 for the count of the minor allele. Logistic regression will be used to test the association between having a minor allele and the log odds of discontinuation of treatment, adjusting for covariates. We plan to enroll 1000 patients and follow them for development of symptoms. Minor allele frequencies reported by Ingle et al. were assumed for the 4 SNPs associated with the TCL1A gene, and preliminary results from the ELPH study were used to estimate minor allele frequencies associated with the ESR gene. A Bonferroni adjustment will be used to account for the simultaneous testing of 10 SNPs; a one-sided p-value of 0.0025 will be considered statistically significant. For purposes of illustrating statistical power, we assume that Hardy-

Weinberg equilibrium exists in the allele distribution and that the minor allele is associated with *higher* proportions of discontinuation of treatment due to development of symptoms. Table 1 shows the genes, SNPs, and representative minor allele frequencies observed in previous studies. Table 2 shows odds ratios for the effect of each minor allele that will be detectable with 80% power for overall discontinuation rates of 20% or 30% and a range of plausible minor allele frequencies, given a sample size of 1000 patients and using a one-sided Cochran-Armitage trend test. The table also shows detectable odds ratios for the subsets of Caucasian (n=600) and African-American and Asian patients (n=200 patients each).

Table 1. SNPs to be validated

SNP	Gene	Rank (Ingle)	Rank (ELPH)	Minor Allele Frequency (MAF)
rs7158782	TCL1A	1		0.189 among cases, 0.109 among controls (0.2 ELPH)
rs7159713	TCL1A	2		0.189 (0.19 ELPH)
rs2369049	TCL1A	3	4	0.176 (.18 ELPH)
rs11849538	TCL1A	4	9	0.15 (ELPH)
rs2296972	HTR2A		1	0.37 (ELPH)
rs2347868	ESR1		2	0.23
rs9340835	ESR1		3	0.35
rs2234693	ESR1			0.45 (Riancho)
rs1062033	CYP19A1			0.44 (Riancho)
rs4646	CYP19A1		5	0.28

Table 2. Odds Ratios for Effect of Each Minor Allele Detectable with 80% Power (Additive Model)

Proportion Discontinuing	MAF	N=1000	N=600	N=200
20%	10%	1.88	2.23	3.89
30%	10%	1.78	2.10	3.65
20%	20%	1.63	1.87	2.94
30%	20%	1.55	1.76	2.70
20%	30%	1.55	1.76	2.66
30%	30%	1.47	1.65	2.42
20%	40%	1.52	1.72	2.59
30%	40%	1.44	1.61	2.33

9.2 Secondary Endpoint Analyses

The association of other SNPs in the ESR, TCL1A, and CYP19A1 genes with discontinuation of treatment due to MSS will be explored using a candidate gene approach. In this exploratory analysis, the prevalence of treatment

discontinuation will be compared between patients who do and do not have the variant genotype, modeling the effects as additive, dominant, and recessive. Correlations among SNPs will be estimated, and linkage disequilibrium among pairs of SNPs will be characterized. Logistic regression models, with treatment discontinuation as the outcome variable, will be used to explore the association with SNPs, adjusting for important clinical factors. No adjustment for multiple comparisons is planned, but only the top ranking SNPs that were not part of the primary validation study will be further explored.

Other endpoints, including the proportions of patients with treatment discontinuation for any reason, the proportion of patients with symptoms determined not to be from other known etiologies, and the proportion of patients whose symptoms improve when the AI is discontinued, will be similarly explored. Time to discontinuation of treatment and time to development of symptoms will be explored using proportional hazards models adjusting for significant genotypic and clinical predictors. Kaplan-Meier plots will be used to graphically portray the associations. Hispanics are the fastest growing demographic group in the US population, and there are 17,100 new breast cancer cases and 2400 breast cancer deaths expected in this demographic group in 2012³⁷. The Hispanic demographic group may have unique attitudes, beliefs and behaviors related to medication adherence with AI.³⁸⁻⁴⁰ Exploratory analyses to determine whether effects are different in patients with Hispanic ethnicity will also be performed.

Previous studies have suggested that patients who experience specific adverse events associated with endocrine therapy may have improved recurrence-free (RFS) and overall survival (OS) compared to those who do not develop these symptoms (42,43). RFS ad OS will be described for the entire study population and for racial and ethnic subsets. Differences in RFS and OS between patients who do or do not develop AIMSS will be explored.

9.3 Statistical Considerations For Patient-Reported Outcomes

Rev. 11/13

Rev. 11/13

We propose to include all 1000 patients in assessment of patient-reported outcomes. Linear mixed effects models will be used to evaluate changes in symptoms over time on these instruments. For purposes of estimating available statistical power, we consider a hypothetical analysis comparing changes in endocrine symptoms from baseline to 3 months between Caucasian and African-American patients. Total score on the FACT-ES (FACT-B plus ES subscale) will be calculated. Psychometric properties of FACT-ES were reported by Fallowfield et al. (29). In that report, mean scores of 61.61 at baseline (standard deviation 6.65) and 57.03 at 12 weeks (standard deviation 9.03) were reported among 32 women (a decline of 4.52 points). Table 3 shows statistical power and differences in change from baseline that will be detectable assuming a two-sided t-test with 5% Type I error, 85% power, baseline standard deviation of 6.65, intrapatient correlations of 0.4 or 0.6, and QOL completion rates of 90% and 75% across the two time points. There will be good power to detect reasonable differences between groups in changes from baseline.

Table 3. Detectable Differences for an Example Patient-Reported Outcomes Analysis (85% Power)

Intra-Patient Correlation	Standard Deviation of Change	Completion Rate	N Caucasian Patients	N African- American Patients	Detectable Difference
0.4	7.285	90%	540	180	1.88
0.6	5.948	90%	540	180	1.54
0.4	7.285	75%	450	150	2.06
0.6	5.948	75%	450	150	1.68

Rev. 11/13

Similar analyses will be done for the FACT-B subscale and for the Trial Outcome Index, consisting of the FACT-B subscale along with the FACT-G Physical Wellbeing and Functional Well-Being subscales.

In E1Z03, the quality of life companion study to MA27, patients who reported being bothered by side effects of treatment were more likely to discontinue treatment. The impact of patient-reported outcomes, both side effects in general and joint pain in particular, on treatment discontinuation will be examined along with the genotype information to assess the relative significance of both.

Patients will be given a choice regarding their preference for submitting QOL instruments in paper form or electronically. If 90% or more of patients choose the electronic system and if the completion rate among those patients is greater than 90%, then the web-based system would be considered for future trials.

If fewer than 90% of patients choose the system but the completion rate among these patients is greater than 90%, then the web-based system would be offered as an alternative in future trials.

If the completion rate among web-based users is significantly lower than the rate for paper forms, then paper forms would be retained for future studies. Assuming that 80% of the 1000 patients opt for the web-based system, there will be adequate power (91%) to detect a difference in completion rates of 12% (for example, 80% vs. 68%), using a one-sided Fisher's exact test with 2.5% Type I error. Given that access issues may exist in racial subgroups, differences in the rates of preference of the on-line system and in the completion rates by racial subgroup will be explored. Within minority subgroups there will be 90% power to detect a difference in completion rates of 28% (for example, 80% vs. 52%) for paper- and web-based processes. A plan to carry electronic capture of QOL data forward would not be considered if this was a barrier to participation in minority communities.

As described in Objective 2.2.6 and Section 6.2.7, a goal of the study is to validate the PROMIS Physical Function (PF) Short Form 20a in patients with AIMSS. We plan to employ both instruments until 480 English-speaking patients have enrolled, assuming that the incidence or AIMSS among these patients is 25%, resulting in 120 symptomatic patients with assessments on both instruments. Validation will include assessment of internal consistency using Cronbach's alpha. Test-retest reliability will be assessed by calculating a bivariate correlation on scores for the first and second administrations among patients whose scores on the HAQ assessment did not change. Associations

between scores on the HAQ and the PROMIS PF20a will be used to evaluate external validity. The ability of the instrument to discriminate between patients with/without symptoms will also be evaluated. Assuming 480 patients, a completion rate of 90% at 3 months, and 25% of patients with symptoms at 3 months, there will be adequate power to detect an effect size of .35, using a twosided t-test with 90% power and 5% Type I error.

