Previous studies by the PI with COBRA investigators identified genetic predictors, such as polymorphisms in estrogen receptors (ESR), or genes encoding for cytochrome P450 enzymes (CYP), of tamoxifen effects. Estrogen receptor subtypes may influence lipid metabolism (13) and bone density (14). Furthermore, CYP polymorphisms are important in predicting discontinuation of tamoxifen (15), and hot flashes (16). Our preliminary data suggest that variants in ESR predict development of AIMSS (Manuscript in preparation). These findings provide an important model for exploration of genetic predictors of side effects of Als. Additional recent work has identified potential genetic determinants of the pharmacokinetics and pharmacodynamics of the Als that may also explain variability in responses to Als. (17-21).

The first evidence for the existence of genetic predictors of AIMSS came from an analysis of 293 cases and 585 controls from the MA.27 trial, a large study which compared exemestane and anastrozole. Genome wide associations (GWAS) and functional genomic studies identified novel single nucleotide polymorphisms (SNPs) and a gene related to IL-17 as associated with AIMSS⁽¹⁷⁾. These findings were recognized as important and should be confirmed in large prospective studies ⁽²²⁾. However, few studies conducted or planned to date have included a predefined phenotype, PROs or specimens evaluable for pharmacogenomics.

Review of available data from the MA27 and the ELPh studies has identified ten SNPs that may be relevant to AIMSS syndrome. In the MA27 dataset, the most striking P values (1E-06) were for three SNPs on chromosome 14, rs7158782, rs7159713, rs2369049, which were all close to the T Cell leukemia 1A (TCL1A) gene, a fourth SNP, rs11849538, was imputed. The ELPh study also identified the latter two SNPs, and four other SNPs. These were rs2296972, the serotonin receptor subtype 2A, rs2347868 and rs9340835 associated with estrogen receptor 1, and rs4646 associated with CYP19A1. An additional two SNPs have been identified in studies of severe large joint arthritis. These are rs2234693 in the ESR1 gene, and rs1062033 in the CYP19A1 gene (22a).

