2.1 Primary Objectives

To validate previously identified associations between 10 specific single nucleotide polymorphisms (SNPs) and discontinuation of treatment with Als due to the development of musculoskeletal symptoms (MSS) among women with breast cancer.

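### Free improvement, not an error: Holm's step-down procedure would validate at least as many of the ten SNPs as the planned single-step Bonferroni rule, at the same implied family-wise level

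*Combined protocol and SAP*

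**What the plan says.** The primary objective (section 2.1) is to validate ten named SNPs as predictors of stopping aromatase inhibitor treatment because of musculoskeletal symptoms. Section 9.1 fits an additive logistic model for each SNP and handles multiplicity in one sentence: "A Bonferroni adjustment will be used to account for the simultaneous testing of 10 SNPs"; "a one-sided p-value of 0.0025 will be considered statistically significant". The family-wise level is not stated; ten tests at 0.0025 imply 0.025 one-sided.

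Table 2 gives odds ratios detectable with 80% power for each SNP, "using a one-sided Cochran-Armitage trend test", at N = 1000, 600 and 200. No step-down procedure is mentioned. No reason is given for a single-step rule, and simultaneous confidence intervals are not planned.

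Table 1 places four of the ten SNPs at TCL1A. Section 1.1.1 says of three of them "which were all close to the T Cell leukemia 1A (TCL1A) gene", and lists a fourth there as imputed. Their correlation is not given; section 9.2 says only that linkage disequilibrium will be characterised.

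**The concern.** Under the planned rule each SNP faces 0.0025 whatever happens to the other nine. Holm orders the ten p-values and compares them in turn with 0.025/10, 0.025/9, and so on to 0.025/1, stopping at the first failure. Its family-wise guarantee is the same and needs no independence assumption, and its rejections always include Bonferroni's.

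The objective asks for a verdict on each SNP, so average per-SNP power is a relevant measure, and that is what Holm can raise. All ten candidates come from earlier data, so more than one true association is plausible. At stake is whether a truly associated SNP that narrowly misses 0.0025 is reported as not validated when the same data and the same error control would allow it to be declared.

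**Working it through.** **Inputs from the documents:** ten hypotheses; one-sided 0.0025 each; 80% power per SNP as the basis of Table 2; N = 1000; 20% or 30% discontinuing; minor allele frequency (MAF) 10-40%; Hardy-Weinberg genotypes; additive coding.

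**Assumed, because the documents do not give them:** family-wise level 0.025; the number of true SNPs (0 to 10 tried); correlation among the four TCL1A test statistics (0, or 0.8).

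**1. Reproduce the plan's figures.** 0.025/10 = 0.0025 exactly. For the trend test under the stated assumptions (normal approximation, case-control variance), all 24 odds ratios in Table 2 give power of 0.805 to 0.819. For example, N = 1000, 20% discontinuing and MAF 20% gives a detectable odds ratio of 1.62, against 1.63 in the table. The plan's power figures stand.

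**2. Holm thresholds.** At step j the threshold is 0.025/(11 - j). A test with 80% power at 0.0025 has mean z of 2.807 + 0.842 = 3.649. Its power at threshold a is 1 - Φ(z(1-a) - 3.649):

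| Step | Rejected before it | Threshold | Power at that threshold |
|---|---|---|---|
| 1 | 0 | 0.00250 | 80.0% |
| 2 | 1 | 0.00278 | 80.9% |
| 4 | 3 | 0.00357 | 83.1% |
| 5 | 4 | 0.00417 | 84.4% |
| 6 | 5 | 0.00500 | 85.8% |
| 8 | 7 | 0.00833 | 89.5% |
| 10 | 9 | 0.02500 | 95.4% |

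A p-value above 0.0025 is therefore helped only when enough other SNPs have already been rejected.

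**3. Compare the two rules.** I simulated 200,000 sets of ten one-sided z-statistics per scenario, with mean 3.649 for true SNPs and 0 for the rest. Where two figures are given, the lower is for correlation 0.8 among the TCL1A statistics and the higher for independence.

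| True SNPs | Average per-SNP power, Bonferroni | Average per-SNP power, Holm | Expected number validated |
|---|---|---|---|
| 1 | 80% | 80% | 0.8 to 0.8 |
| 2 | 80% | 80.7-80.8% | 1.6 to 1.6 |
| 4 | 80% | 81.8-82.5% | 3.2 to 3.3 |
| 6 | 80% | 84.2-84.7% | 4.8 to 5.1 |
| 8 | 80% | 87.1-87.8% | 6.4 to 7.0 |
| 10 | 80% | 91.8-92.7% | 8.0 to 9.2-9.3 |

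Holm kept every Bonferroni rejection in every set. The chance of validating at least one true SNP was the same to within about 0.02 percentage points, because the first Holm step is the Bonferroni test. With independent statistics and 50% power per true SNP, the gains are about 0, 0.7, 2.3, 7 and 11 points for one, two, four, eight and ten true SNPs.

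**4. Family-wise error.** With no true SNP and independence, both rules give 1 - (1 - 0.0025)^10 = 2.47%. With some true SNPs, Bonferroni against Holm is:
- one true, independent statistics: about 2.3% against 2.5%
- four true: about 1.5% against 2.2%
- eight true: about 0.5% against 1.8-1.9%

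Both stay within 2.5% throughout.

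**The case against.** The planned rule is valid, pre-specified and consistent with its own power table. Nothing in Table 2 or the sample size is wrong, and neither would change under Holm.

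The largest gain needs all ten SNPs to be true. The documents give no such number and offer some reason to expect fewer: two SNPs come from work on severe large-joint arthritis and have no rank in either aromatase inhibitor study in Table 1, and four others sit at one locus. With two to four true SNPs the gain is only about 1 to 2.5 points.

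Bonferroni also has real merits: one threshold per SNP that does not depend on the others, simple matching confidence bounds, and fewer false validations when some SNPs are true.

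Most of this stands, and it is why the point is an improvement and not a defect. A reader might infer that the plan gives up power for nothing. The documents do not support that: the loss depends on an unstated number of true SNPs, and Bonferroni's lower realised error is a return of a kind. It does come from leaving part of the permitted 2.5% unused, and the plan claims none of these merits as its reason.

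A reader might also infer that any SNP with p between 0.0025 and 0.005 is lost because of the single-step rule. That is too strong: Holm reaches 0.005 only after five other SNPs are rejected, and 0.00417 after four.

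**Conclusion.** Section 9.1 uses a correct but less powerful procedure than one available at the same implied family-wise level. That Holm controls the level under any dependence and never rejects less is a theorem. The size of the gain is conditional: with 80% power per true SNP at 0.0025, it is nil with one true SNP, under 1 point with two, about 2 to 2.5 with four, 4 to 5 with six, 7 to 8 with eight, and 12 to 13 only if all ten are true. It is never negative, and it does not alter the chance of validating at least one SNP. These sizes rest on an assumed number of true SNPs, equal power for each, an assumed TCL1A correlation, and the inferred 0.025. They do not show that the primary analysis is invalid or underpowered against its own table.

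**What to change.** In section 9.1, replace the Bonferroni sentence with: 'The ten one-sided p-values will be tested with the Holm step-down procedure at family-wise one-sided level 0.025.' This also states the family-wise level, which is now only implied. Keep Table 2 and label it as power at the first Holm step, hence a lower bound for each SNP. Make the change before any genotype-outcome results are seen; adopting Holm afterwards to admit a SNP that missed 0.0025 would not be credible.

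The cost is one sentence and one table note. It needs no more patients, data or modelling, and family-wise control at 0.025 is kept. If the team prefers a single fixed threshold, for example to report matching simultaneous bounds, stating that reason in 9.1 would also settle the point.
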